tDCS for Chronic Low Back Pain: A Study Examining the Effect of Transcranial Direct Current Stimulation on the Emotional Response to Chronic Low Back Pain

Principal Investigator:

[name]., Ph.D.

STUDY DESCRIPTION

The goal of this study is to investigate the role of central neural pathways in mediating chronic pain. The aim of the study is to test the effect of stimulating brain regions that are part of a network underlying central pain processing using a non-invasive brain stimulation technique, transcranial Direct Current Stimulation (tDCS). Prior studies have used tDCS to target both sensory related cortical areas (Fregni 2006) and those important for higher-order representations of pain (Mendonca 2011). This study will target brain regions important for the behavioral response to the chronic sensation of pain. The hypothesis is that stimulation of these brain regions can modulate not only the affective component of pain, but ultimately also improve functioning and quality of life. This hypothesis will be tested by treating study participants eighteen and older with chronic low back pain (CLBP) of greater than six months using tDCS. To be part of this study, participants must be Veterans that meet all the inclusion and exclusion criteria.

Specific Aims:

The aim of the proposed study is to determine effects of tDCS on the affective and behavioral component of chronic pain. The study will specifically target the dorsal anterior cingulate cortex (dACC), an important component of brain circuits that mediate learning in response to emotionally charged experiences. Measures of distress will be obtained due to the sensory component of pain to assess the degree to which pain interferes with the participants' daily activities and the emotional impact of CLBP on their lives.

Aim 1

To test the acute effects of active vs. sham cathodal (inhibitory) tDCS over dorsal anterior cingulate cortex (dACC), a region implicated in the affective components of pain in forty (40) patients in a controlled design.

Aim 2

To test the longer term effects of active vs. sham cathodal (inhibitory) tDCS over dACC in the same forty (40) patients in a controlled design.

Hypotheses:

Acute effects:

Hypothesis 1.1:

Distress associated with pain as measured by the West Haven-Yale Multidimensional Pain Inventory (WHYMPI) (affective subscale) and pain anxiety symptom scale (PASS-20) will decrease after ten (10) days of active, but not sham stimulation.

Hypothesis 1.2:

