stimulation of brain regions underlying the emotional component of pain, with the goal of interrupting the continuation and reinforcement of this cycle of maladaptive behavior.

Multiple interconnected brain regions are implicated in pain processing (Mackey 2004; Borsook 2010). These include areas of the brain directly responsible for processing sensory input such as the thalamus, primary and secondary somatosensory cortices, and regions important for mediating cognitive aspects of pain processing, such as dorsolateral prefrontal cortex (DLPFC), dorsal anterior cingulate cortex (dACC), medial and ventromedial prefrontal (mPFC and vmPFC, respectively), orbitofrontal (OFC), and insular cortex. The investigators will target those brain regions that play a role in emotional salience of pain processing. Specifically, our initial efforts will inhibit the activation of dACC. We posit that reducing the activity in dACC will decrease the emotional saliency of pain, impacting the degree to which CLBP causes disability.

The role of anterior cingulate cortex (ACC) in mediating pain processing is well supported. First, a mainstay treatment for chronic pain includes opioid medications. Though these medications act in multiple brain regions, ACC exhibits one of the highest densities of opioid receptors in the brain and is a primary site of action for these treatments (Vogt 1995). Second, selective surgical lesion of the cingulate cortex has been used to treat chronic pain since the 1960s. Importantly, following surgery, though patients reported still experiencing the pain, they were less bothered by it (Eisenberger 2004; Folz 1968). This response supports the role of ACC in the affective component of pain processing. It is the goal of this study to determine whether a similar dissociation between the sensation of pain and the distress related to pain can be elicited by stimulating dACC using a non-invasive method, tDCS.

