The participant will then receive either the sham or active tDCS stimulation based on their random group assignment for twenty minutes (tDCS details are below). Following tDCS stimulation, only the DVPRS will be repeated. This measure will be used to determine whether immediate pain relief following stimulation occurs. Lastly, in order to monitor the effectiveness of the blind, participants will be asked to guess which treatment, active or sham, they received.

On subsequent treatment days, the DVPRS will be repeated before and after stimulation and the Sleep Measure will be repeated before stimulation.

At the end of the first week of treatment, session five, in addition to the DVPRS and the Sleep Measure, the WHY-MPI, RMDQ, PHQ-9, GAD-7, PASS, and CPAQ-8 will be repeated.

During the second week, the DVPRS will again be administered before and after each treatment, and the Sleep measure will be repeated before stimulation

On the final day of treatment, in addition to the DVPRS and the Sleep Measure, the WHYMPI, RMDQ, PHQ-9, GAD-7, CEQ, CSQ-8, PASS, and CPAQ-8 will be repeated.

Follow-up assessments will occur by phone approximately six (6) weeks after the last tDCS treatment session and will consist of the same measures as session ten.

tDCS details:

Equipment used for tDCS Intervention, the Neuroconn DC-STIMULATOR PLUS, is a micro-processor-controlled constant current source. tDCS is a non-invasive procedure in which a device sends a small Direct Current (DC) across the scalp to modulate brain function. A lowlevel current from the positive electrode, anode, is sent to the negative electrode, cathode. When the extremely low level current passes from the anode to the cathode, it may simultaneously increase the activity of the brain by the anode and decrease the activity of the brain near the cathode. The DC-stimulator meets the highest safety standards thanks to (hardware- and software-based) multistage monitoring of the current path. It continuously monitors electrode impedance and it can detect insufficient contact with the skin and automatically terminate stimulation to reliably prevent participant injury.

The FDA recognizes the tDCS device as a non-significant risk device. During each treatment session, tDCS will be applied to the scalp using a Neuroconn DC- Stimulator Plus (Figure 1).

Figure 1. tDCS device

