Stimulation will be applied to the participant's skull using metal electrodes seated in a flat, slightly perforated rectangular sponge pocket. The sponges will be soaked in normal saline (0.9% NaCl) and affixed to the head on intact skin (after the scalp skin is cleaned with an alcohol prep pad) and held in place with a custom tDCS specific rubber headband. One set of sponges will be used for each participant. Standard conductive water based gel (Spectra 360 electrode gel) will be applied to the sponge (between the scalp and the sponge) only if the impedance is found not to be optimal, to improve current flow. In this experiment, only 1 stimulating electrode and 1 reference electrode will be used. The investigators will target the dorsal anterior cingulate cortex by placing the stimulating electrode at FC₁ on the 10-20 EEG system (see Figure 2). The reference electrode will be placed on the contralateral supra-auricular point, at T₃ (see Figure 3). Point T₃ will be located immediately above the superior tip of the participant's pinna. Point FC₁ will be located via scalp measurements: 50% of the way from the participant's nasion to inion will be used as reference point C_z (see Figure 2), 33% from the nasion to inion will be used as point F_z, and 50% of the way from T₃ to C_z will be used as C₃. FC₁ will be 50% of the way from C₃ to F_z. Active tDCS, i.e. anodal or cathodal, will be applied during the session. The device will deliver a maximum of 2 mA (2.55 mA/cm²) of direct current stimulation for twenty (20) minutes which is controlled by a timer on the device.

[figure not shown]

Figure 2. 10-20 EEG System

[figure not shown]

Figure 3. 10-20 EEG System

In the sham condition, the current paradigm will consist of 40 seconds of stimulation at 1mA and then 19 minutes and 20 seconds of stimulation averaging no more than 0.002mA. This procedure allows for participants to detect the associated tingling sensation at the beginning of the session, making participants more likely to believe that they are receiving active stimulation and the short duration is not expected to have any effect on brain function.

HUMAN SUBJECT PROTECTION

Potential Risks and Discomforts

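### The stimulation setup contradicts itself on the return electrode, called contralateral but placed at T3 on the FC1 side, and is loose on polarity where the aims are cathodal only

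*Combined protocol and SAP*

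**What the plan says.** The setup is specified under tDCS details. There are two electrodes, one stimulating and one reference. The stimulating electrode goes at FC1 in order to target dACC. For the other, "The reference electrode will be placed on the contralateral supra-auricular point, at T₃". T3 is located just above the tip of the pinna. Cz and Fz are set at 50% and 33% of the distance from nasion to inion. Then "50% of the way from T₃ to C_z will be used as C₃", and "FC₁ will be 50% of the way from C₃ to F_z".

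On polarity the same section says "Active tDCS, i.e. anodal or cathodal, will be applied during the session". It gives no rule for choosing, and it names the electrodes only as stimulating and reference. It also explains that when current flows, "it may simultaneously increase the activity of the brain by the anode and decrease the activity of the brain near the cathode".

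Elsewhere the polarity is single. Aim 2 reads "To test the longer term effects of active vs. sham cathodal (inhibitory) tDCS over dACC", and Aim 1 uses the same description for the acute effects. The Background says "Specifically, our initial efforts will inhibit the activation of dACC". The section on management of risks due to tDCS treats cathodal stimulation as crucial to the design. The Research Plan has one active and one sham arm, with no anodal arm.

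**The concern.** The trial asks whether inhibiting dACC reduces the distress and disability that go with chronic low back pain. The result can be read that way only if the setup is known: which electrode is the cathode, and where the current returns. The list of the tDCS operator's duties requires positioning and parameters to follow the protocol and forbids the operator to revise them independently. The tDCS details are therefore operating instructions, and a contradiction there is more than clerical.

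The return electrode matters most. One half of the sentence sends it to the side opposite the stimulating electrode, and the other half names a site on the same side. Operators who followed different halves would use different current paths. The polarity wording comes second. By the protocol's own account the anode and cathode may act in opposite directions, so an instruction that admits both does not match aims that admit one.

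**Working it through.** **Return electrode: which side is FC1 on?** All inputs come from the tDCS details.

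Let x be the left-right coordinate, with the midline at 0 and T3 at -1.

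- Cz and Fz are both measured along the nasion-inion line, so x = 0 for each.
- C3 is halfway from T3 to Cz: x = (-1 + 0)/2 = -0.5.
- FC1 is halfway from C3 to Fz: x = (-0.5 + 0)/2 = -0.25.

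FC1 has the same sign as T3. These are straight-line midpoints, but the sign needs no head model: a point halfway between a T3-side point and a midline point stays on the T3 side. The only other electrode is the one at FC1, so contralateral naturally means opposite FC1, and T3 is not.

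**How different are the two readings?** This step needs an assumption, because the documents give no head dimensions. Take a unit sphere with Cz at the top, a nasion-inion arc of 180 degrees, and the ear point at angle e from Cz.

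- Fz lies (50% - 33%) x 180 = 30.6 degrees in front of Cz.
- C3 = (-sin(e/2), 0, cos(e/2)).
- FC1 = (C3 + Fz) / |C3 + Fz|.

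For e = 90 degrees:

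- C3 = (-0.707, 0, 0.707) and Fz = (0, 0.509, 0.861).
- Their sum is (-0.707, 0.509, 1.568), of length 1.794, so FC1 = (-0.394, 0.284, 0.874).
- Angle from FC1 to T3: arccos(0.394) = 66.8 degrees.
- Angle from FC1 to the opposite ear point: arccos(-0.394) = 113.2 degrees.
- Ratio along the scalp: 113.2/66.8 = 1.70 (1.695 before rounding).
- Ratio in a straight line: sin(56.6)/sin(33.4) = 1.52.

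| Ear point from Cz (degrees) | FC1 x-coordinate | FC1 to T3 (degrees) | FC1 to opposite ear point (degrees) | Ratio along scalp | Straight-line ratio |
|---|---|---|---|---|---|
| 72 | -0.319 | 54.3 | 91.3 | 1.68 | 1.57 |
| 80 | -0.353 | 59.8 | 101.1 | 1.69 | 1.55 |
| 90 | -0.394 | 66.8 | 113.2 | 1.70 | 1.52 |

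Varying the ear point from 70 to 100 degrees and the nasion-inion arc from 160 to 220 degrees gives scalp ratios of 1.68 to 1.71, straight-line ratios of 1.47 to 1.58, and an FC1 coordinate of -0.31 to -0.44. FC1 is always on the T3 side. The ratios do not depend on head size.

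**Polarity: the statements side by side.** No arithmetic applies.

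| Place | Polarity |
|---|---|
| Specific Aims, Aims 1 and 2 | Cathodal (inhibitory) |
| Background | Inhibit dACC |
| Management of risks due to tDCS | Cathodal, crucial to the design |
| tDCS details | Anodal or cathodal |

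The aims put cathodal stimulation over dACC, and the tDCS details target dACC with the stimulating electrode at FC1. Together these place the cathode at FC1. The reader has to combine two sections to get there.

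**The case against.** **Polarity.** The strongest reply is that the protocol, read as a whole, specifies it. The operator's duties point to the whole protocol, aims included, and one item has the attending physician establish the parameters. The loose phrase may only have been meant to define active stimulation as opposed to sham. This largely stands. A reader might infer that the inhibitory setup cannot be confirmed from the protocol, or that some participants received anodal stimulation. The documents support neither: the intended cathode at FC1 is recoverable, there is no anodal arm, and nothing reports anodal delivery. What remains is a conflict of wording in the section operators work from.

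**Return electrode.** It can be said that the instruction names T3, gives a landmark for it and refers to Figure 3, so that contralateral is one stray word. That may be right, but the text alone does not show whether the word or the label is the mistake. Figure 3 is missing from the copy reviewed, which is no fault of the plan. It may show the intended site, so it would be wrong to infer that operators had no single setup to follow. Even so, no figure could make the sentence agree with the construction of FC1.

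**Size.** The distance ratios connect to no outcome in the documents. This is also correct. They show only that the two readings are distinct montages.

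**Conclusion.** The return-electrode instruction is wrong as written: T3 is ipsilateral to FC1 by the protocol's own measurements, so the sentence describes two montages. That conclusion needs no assumption beyond taking contralateral to mean opposite the stimulating electrode. The size of the difference, about 1.7 times along the scalp and about 1.5 to 1.6 times in a straight line over ear points of 72 to 90 degrees, rests on the spherical head.

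The polarity wording is a lesser inconsistency with a recoverable answer. A reader might go on to infer a loss of power or a biased treatment difference. The documents give no figure linking polarity or return site to any outcome, so neither is claimed. The correction should be made because the text governs delivery of the only active treatment and costs almost nothing to put right.

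**What to change.** In the tDCS details:

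- State one setup: cathode at FC1, anode (reference) at one named site. Delete the words that allow anodal stimulation.
- Settle the return side. Either delete contralateral and keep T3, or name the supra-auricular point on the opposite side as the reference and keep T3 only as the landmark for C3.
- Make Figure 3 agree.
- Leave the current and duration as they are. The protocol sets 2 mA as a maximum for twenty minutes, and this correction gives no reason to turn a ceiling into a fixed dose.

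If treatment has started, report the montage and polarity actually used, as far as available records or operator confirmation allow. The documents do not require either to be recorded, so the answer may be incomplete. Include the parallel-study data pooled under Appendix B if the information can be obtained. Those data arrive de-identified in a single one-way transfer, so it may have to be asked of that study directly.

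The cost is about two sentences of protocol wording, a check of one figure and, if treatment has begun, an enquiry to those who delivered it. No visits, participants or measures are added.

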Screening is expected to take approximately one and a half (1 ½) to two hours (2). The principal investigator/s will make the ultimate determination of whether the participant meets all the enrollment criteria and is appropriate to enter the study. Participants that do not meet the study criteria will be informed that based on the information collected, it has been determined they are not appropriate for the current study. Appropriate referrals will be made to other health care providers, at the VA or to outside providers, if desired by the participant.

RESEARCH PLAN

After the potential participant signs the consent form, is screened, found eligible and states they are still interested, they will be enrolled into the study. The study includes a screening visit, ten (10) study treatment session visits on consecutive weekdays and a follow-up phone call, approximately six (6) weeks after the last study visit. The ten study visits will occur at the

PVAMC and will take approximately one (1) to one and a half hours (1 ½) hours. The follow-up phone call will take about one (1) hour. The total duration of this study for the participant is expected to be approximately eighteen (18) hours; this includes the consent process, screening and eligibility assessments, and ten research visits which will include the study treatment, tDCS, completion of study related questionnaires, and the follow-up phone call.

Half of the participants will receive only sham stimulation for all treatment days (days where tDCS is applied) and half will receive only active stimulation; this will be randomly assigned. Comprehensive measures of distress resulting from CLBP will be administered to assess both the short and longer term effects of tDCS treatment. Participants and research staff administering outcome scales will be blinded to active vs. sham tDCS.

Specific Procedures:

Questionnaires

Table 1, below identifies the schedule for when the study questionnaires will be used. All questionnaires will be done with assistance of blinded study personnel.

Pain Severity:

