We will assess treatment credibility and patient expectations for treatment success using the Credibility Expectancy Questionnaire (CEQ; Devilly & Borkovec 2000). The Client Satisfaction Questionnaire-8 (CSQ-8; Larsen, Attkisson, Hargreaves, & al., 1979), an 8-item scale, will be used at post-treatment to assess patient satisfaction with the treatment. This scale has acceptable psychometric properties (Nguyen, Attkisson, & Stegner, 1983).

Psychiatric History:

Drug related problems, exclusionary disorders, and other non-exclusionary psychiatric disorders will be assessed with a structured psychiatric interview, the Mini International Neuropsychiatric Interview (M.I.N.I.) for the DSM-IV. This is a validated interview designed to screen for Axis I disorders. Potential participants determined by the M.I.N.I. to have lifetime diagnoses of bipolar disorder, schizophrenia, other chronic psychotic condition(s), and/or current drug or alcohol dependence will be considered screen failures.

Sleep Measure

An in-office assisted report of sleep will be used to assess quantity and quality of sleep throughout the ten testing days of the study. The questions used to assess sleep have been based on those used in the 1992 Carskadon Sleep-Wake Diary.

Table 1. Schedule of Assessments

	Purpose	Consent and Screen	First Day of Week One Session 1	Pre/Post Treatment Session 1-10	End of Week One and Two Session 5 & 10	Six Week Follow-up
Pain Severity Defense & Veterans Pain Rating Scale (DVPRS)	I, O	X	X	X	X	X
Pain Interference WHY-MPI RMDQ	O O		X X		X X	X X

Emotional Distress PHQ-9 (Depression) GAD-7 (Anxiety) PASS-20 (Pain related fear/avoidance) CPAQ-8 (affective dimension of pain)	O O O O		X X X X		X X X X	X X X X
Psychiatric History M.I.N.I.	I	X				
Sleep Measure Sleep assessment	O		X	X	X	X
Patient Expectation and Satisfaction CEQ CSQ-8	T T		X X		X* X*	 *(only session 10)

Assessment instruments are used for the following purposes:

I= Inclusion criteria; T = Treatment Development Target Assessment; O = Outcome Measure

Links to the measures, when available:

[DVPRS](#)

[WHY-MPI](#)

[RMDQ](#)

[PHQ-9](#)

[GAD-7](#)

[PASS-20](#)

[CEQ](#)

[CSQ-8](#)

Study Visits

All participants will be clearly directed to the building and room where the study procedures will occur prior to each visit. All study visits will occur at PVAMC in Building 1 or at the Neurorestoration Center, Building 32, in a research exam room as assigned.

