On the first day of treatment, prior to the tDCS treatment, females of childbearing age will be required to have a urine pregnancy test before any study procedures. The female participant will be brought to the PVAMC laboratory where the clinical laboratory staff will be handling and processing the participant's urine, do the pregnancy testing, and report the results as part of their daily clinical responsibilities. The pregnancy test will be done through the PVAMC laboratory according to their standard of practice. Research key personnel will not handle or have contact with the participant's urine for this pregnancy test. Participants are informed in the study consent form of this requirement to give permission for a pregnancy test to be involved in this study and

that the results will be recorded in their PVAMC medical record. Any participants that show a positive pregnancy test will be considered a screen failure.

Participants will be asked to complete the DVPRS, WHY-MPI, RMDQ, PHQ-9, GAD-7, PASS, CPAQ-8, CEQ, CSQ-8, and the Sleep Measure. This will provide a baseline measure in regards to the sensory/perceptual component of their pain, the degree to which pain interferes with daily activity, and the emotional component of their pain.

Prior to this and each study treatment, designated research staff will assess the skin on the participant's scalp where the electrodes will be placed to assure there are no lesions, cuts, or exclusionary skin disorders. Participants will be positioned for optimal comfort on a chair, recliner, or stretcher. Designated trained research staff will attach the electrodes to the participant's scalp (participants will not need to have any hair shaved) and apply the flexible rubber headband to keep them in place (see detail below). Participants will be educated that research staff will be monitoring them continuously through a non-recording closed-circuit camera from another room or he/she will be physically present in the room to assess if they need anything or want to stop the tDCS.

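### Sham opens at 1 mA while the only active current stated is a maximum of 2 mA; matching the 40-second onset is a cheap improvement to the blind

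*Combined protocol and SAP*

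**What the plan says.** The stimulation settings are under tDCS details. For active: "The device will deliver a maximum of 2 mA", with a density of 2.55 mA/cm² and a duration of 20 minutes. For sham: "40 seconds of stimulation at 1mA and then 19 minutes and 20 seconds of stimulation averaging no more than 0.002mA". The protocol gives the purpose of the sham onset as "making participants more likely to believe that they are receiving active stimulation". It argues that sham is inert on the ground that "the short duration is not expected to have any effect on brain function". It does not explain the 1 mA level, fix an active current below the maximum, or describe a ramp in either arm.

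Several other provisions bear on the point:

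- **Research Plan:** "Half of the participants will receive only sham stimulation for all treatment days", and the other half receive only active. Participants and the staff who administer the outcome scales are blinded.
- **Study Visits, first treatment day:** after stimulation, "in order to monitor the effectiveness of the blind, participants will be asked to guess which treatment, active or sham, they received". The descriptions of later sessions do not mention a guess.
- **Patient Expectation and Satisfaction:** "We will assess treatment credibility and patient expectations for treatment success using the Credibility Expectancy Questionnaire". On day one this questionnaire (CEQ) belongs to the baseline set completed before stimulation: "Participants will be asked to complete the DVPRS, WHY-MPI, RMDQ, PHQ-9, GAD-7, PASS, CPAQ-8, CEQ, CSQ-8, and the Sleep Measure". It is repeated at session 10. Study Visits has follow-up repeat the session-ten measures, whereas the note in Table 1 appears to limit the repeat CEQ to session 10.
- **Appendix B:** de-identified data from a parallel hospital study will be combined with this study's data and analysed together. That study's sham settings are not given.

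**The concern.** A sham onset protects the blind only if it feels enough like the start of an active session. Here its current is set at half the only active level that the protocol states. If a weaker current gives a weaker tingle, sham participants have a cue to their allocation at each of ten sessions.

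The pain, interference, distress, acceptance and sleep outcomes in Table 1 are participant-reported, so belief about allocation can affect them. Hypotheses 1.1 and 1.2 predict improvement on active but not on sham. A difference in belief caused by a weaker sham cue would push results in that same direction.

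**Working it through.** **Inputs, all from tDCS details.** Active: at most 2 mA for 20 min, at 2.55 mA/cm². Sham: 1 mA for 40 s, then 19 min 20 s at no more than 0.002 mA on average. The delivered active current is not fixed, so I take an assumed range of 1 to 2 mA. No ramp is described, so active is treated as constant throughout the session.

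**Session length.** 40 s + (19 × 60 + 20) s = 40 + 1,160 = 1,200 s = 20 min. The sham session equals the active session in length, as the protocol intends.

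**Formulas.** Onset ratio = 1 mA / active current. Charge (mC) = current (mA) × time (s).

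- Planned sham charge: 40 × 1 + 1,160 × 0.002 = 40 + 2.32 = 42.32 mC.
- Matched sham charge: 40 × active current + 2.32 mC.
- Active charge: 1,200 × active current.

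| Active current | Onset ratio as planned | Active charge | Planned sham, % of active | Matched sham charge | Matched sham, % of active |
|---|---|---|---|---|---|
| 2 mA | 1/2 = 50% | 2,400 mC | 42.32/2,400 = 1.8% | 82.32 mC | 3.4% |
| 1.5 mA | 1/1.5 = 67% | 1,800 mC | 42.32/1,800 = 2.4% | 62.32 mC | 3.5% |
| 1 mA | 1/1 = 100% | 1,200 mC | 42.32/1,200 = 3.5% | 42.32 mC | 3.5% |

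The matched percentage barely moves because it is mostly 40/1,200 = 3.3%. Charge describes the cost of the change. It does not measure blinding.

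**Ten sessions at 2 mA.** Planned sham is 0.42 C and matched sham 0.82 C, against 24 C for active.

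**Current density.** 2 / 2.55 = 0.784 cm², so a 1 mA onset is 1 / 0.784 = about 1.28 mA/cm², and a matched 2 mA onset is 2.55 mA/cm² for 40 s. Management of Risks due to tDCS reports nothing worse than tingling and transient redness at up to 2.56 mA/cm² for up to 22 minutes. That evidence is from arm skin, not scalp.

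**Drop after 40 s.** From 1 to 0.002 mA as planned (0.998 mA), and from 2 to 0.002 mA if matched at 2 mA (1.998 mA).

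**The case against.** The strongest objection is that no harm is shown. Nothing in the protocol says that 1 mA feels different from 2 mA, and its rationale is that the brief 1 mA onset is itself detectable. Each participant receives one condition only, so nobody compares the two onsets. The guess and the CEQ monitor belief, and the study is exploratory and pilot-funded. This stands as far as size is concerned: neither the loss of blinding nor any bias can be derived. It does not supply a reason for the lower onset. A faint, brief sensation can suggest sham without a side-by-side comparison.

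Monitoring also detects a problem only afterwards, and coarsely. With the 20 per arm planned at this site and guess rates near 50% (assumed), the 95% interval for the difference between arms is about ±1.96 × √(2 × 0.25/20) = ±31 percentage points.

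Second, the comparator is only a maximum. If active ramps up, its first seconds are below its plateau; if it runs at 1 mA, there is no mismatch. This stands, and it is why the 50% figure is conditional.

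Third, matching the onset leaves 19 min 20 s in which active continues and sham is near zero, and it enlarges the drop in current, which could itself be noticed. This stands as a downside of unknown size.

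Fourth, changing the sham at this site alone could put two different shams into one pooled control group under Appendix B. This stands and alters the fix.

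**Conclusion.** The point holds as a low-cost improvement to a workable sham. At the 2 mA maximum, the sham cue is delivered at 50% of the active current without explanation. The ratio is 67% at 1.5 mA and 100% at 1 mA. These figures assume a constant active current with no ramp.

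A reader might infer that the blind is broken, that the results will be biased, or that the sham always opens at half the active level. The documents support none of these. They give no sensation data and no fixed active current, and no participant receives both conditions. Nor is this an error in a stated figure: the sham timings add up to 20 minutes. The case for acting is that the change serves the protocol's own purpose for the onset, protects participant-reported outcomes, and leaves intact the short duration on which the inertness argument rests. The charge ratio alone does not prove that a matched sham is inert.

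**What to change.** State the active current and any ramp. Set the 40 s sham onset to the same peak current and the same ramp, then drop to no more than 0.002 mA for the rest of the 20 minutes.

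Settle this with the parallel study in Appendix B. If it is still treating participants, use the same sham there. If not, record sham version and site for every participant and include this as a factor in the pooled analysis. Because sham version affects controls only, the active-versus-sham contrast should be allowed to differ by version or site; a site main effect alone would not capture it. Record the version in the same way if anyone at this site has already been treated under the present setting.

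**Cost.** One stimulator setting and one or two protocol sentences, with no added visits, staff or session time. Management of Risks due to tDCS says that the device is adjustable in intensity and duration; confirm that the sham onset can be set separately. The downsides are brief active-level tingling in sham, 40 mC more sham charge per session at 2 mA (82.3 instead of 42.3 mC), a larger drop in current after 40 s, and the work of coordinating with, or accounting for, the pooled study.
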